3.3 Secondary objectives

- To compare the safety of OVD PRO-149 versus Healon® EndoCoat in cataract phacoemulsification surgery and intraocular lens implantation, with the incidence of AEs.
- To compare the safety of OVD PRO-149 versus Healon® EndoCoat in cataract phacoemulsification surgery and intraocular lens implantation, through changes in central corneal thickness.
- To compare the safety of OVD PRO-149 versus Healon® EndoCoat in cataract phacoemulsification surgery and intraocular lens implantation, with the presence of cellularity in postoperative AC.
- To compare the safety of OVD PRO-149 versus Healon® EndoCoat in cataract phacoemulsification surgery and intraocular lens implantation, with the presence of postoperative AC flare.
- To compare the best-corrected visual acuity obtained after cataract phacoemulsification surgery and intraocular lens implantation between PRO-149 and Healon® EndoCoat.

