7.4.4 Definition of variables, methods and scales to be used for measurement

Variable	Guy	Unit (symbol)	Measurement method	Normal value	Evaluation time	Statistical test
Of outcome primary						
Endothelial cell count (cornea)	Continuous quantitative	Cells / mm^2	Microscopy speculate	1500-3500	VE and VF	Student t - test Mann-Whitney U Wilcoxon ranks *
Intraocular Pressure	Continuous quantitative	mmHg	Goldmann tonometry	10-21	VE, V1, V2 and VF	Student t test Mann-Whitney U Wilcoxon ranks *
Of outcome secondary						
Events adverse	Discreet	Number of cases (n)	Counting	0	VE, VP, VC, V1, V2 and VF	Student t test Mann-Whitney U*

Events adverse (Bis)	Nominal categorical	Present / Absent	Observation	Absent	VE, VP, VC, V1, V2 and VF	χ^2 or Fisher's exact test
Changes in corneal thickness	Continuous quantitative	μm	Corneal pachymetry	545 ± 40	VE and VF	McNemar test **
Cellularity of the anterior chamber	Qualitative ordinal	Degrees	Biomicroscopy	0= None	VE, V1, V2 and VF	χ^2 or Fisher's exact test
Flare in the anterior chamber	Qualitative ordinal	Degrees	Biomicroscopy	0= No flare	VE, V1, V2 and VF	McNemar test **
AVMC	Discreet	Fraction (-)	Snellen chart	0.6-2.0	VE, V1, V2 and VF	χ^2 or Fisher's exact test
Of outcome exploratory						
Transsurgical evaluation	Qualitative ordinal	Bad (0) / Very good (5)	Observation	...	VC	χ^2 or Fisher's exact test

BCVA, best-corrected visual acuity; ScrV, scrutiny visit; SurV, surgery visit; SchV, scheduling visit; V1-2, 1st / 2nd safety visits; VF, final visit; χ^2 , Chi-square; *For KS/SW, p < 0.05; **When applied

Table 3. Operational definition of variables

The variables, method, and scales used to measure them are described in detail below. They are listed in order according to **Table 3**.

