7.4.4.5 Cellularity and flare in the anterior chamber

In the presence of intraocular inflammation, increased permeability of the non-pigmented layer of the ciliary epithelium, the posterior iris epithelium, and the iris vascular endothelium results in the accumulation of cells and proteins (visible to the examiner as flare) in the anterior chamber. Using a 0.2mm X 0.2mm light beam directed obliquely into the anterior chamber with a forward tilt of the light source (slit lamp tower), the degree of flare and cellularity will be determined according to the Uveitis Nomenclature Standardization Working Group. [35] The degree of agreement will be reported in the eCRF according to the given grade (See **Table 4** and **Table 5**).

Table 4. Scale for anterior chamber cellularity

Degree	Number of cells
0	None
½ +	1-5
1 +	6-15
2 +	16-25
3 +	26-60
4 +	More than 60

Visible in a 0.2mm x 0.2mm field

Table 5. Flare scale

Degree	Number of cells
0	There is no flare
1 +	Mild
2 +	Moderate (iris and lens clearly visible)
3 +	Marked (iris and lens slightly blurred)
4 +	More than 60 (fibrin)

Management as AE: Reported values ≥ 3 for cellularity or flare should be reported as AE.

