7.4.4.7 Transsurgical evaluation

During the surgical procedure, the surgeon will assess the clinical behavior of the PI. Immediately after completing the procedure, he or she will answer the questionnaire "Evaluation of OVD performance", appendix 15.1. The ability of the OVD to maintain the AC formed during continuous circular capsulorhexis (CCC) and IOL implantation, retention during phacoemulsification, ease of use (including blister removal, syringe assembly, ease of injection), ergonomics, facilitation of CCC performance, transparency during surgery, and ease of removal will be evaluated. They will be graded on a 5-point scale: 0 = very poor; 1 = poor; 2 = acceptable; 3 = good; 4 = very good. The results will be recorded in the eCRF.

Management as AE: Not applicable. The results of this questionnaire should not be considered AE.

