10.1.2 Data interpretation

The results of continuous quantitative variables will be presented in measures of central tendency: mean, standard deviation and ranges.

KS and SW tests will be performed, as applicable, to determine whether the distribution presents normality in the results obtained in each study group. [44]

If normality of the data is observed ($p > 0.05$; for KS and SW), the statistical analysis of the continuous quantitative variables to find significant differences (p) will be as follows:

- Intra-group analysis: will be determined using the Student's t-test for repeated measures.
- Between-group analysis: differences between groups will be analyzed using Student's t-test for independent groups.

For $p < 0.05$ in KS and SW, the statistical analysis of continuous quantitative variables to find significant differences (p) will be as follows:

- Intra-group analysis: will be determined using the Wilcoxon rank test. [45]
- Between-group analysis: differences between groups will be analyzed using the Mann-Whitney U statistic.

The level of difference to consider significance will be an α of 0.05 or less [46].

The results of the nominal and ordinal qualitative variables will be presented in frequencies, proportions and percentages.

Statistical analysis to identify significant differences in qualitative variables will be performed by creating 2x2 contingency tables and will be carried out as follows:

- Intra-group differences: will be determined by the McNemar test [47], which is applied to 2x2 contingency tables with a dichotomous trait and pairs of matched subjects to determine whether the marginal frequencies of row and column are equal (marginal homogeneity).
- Difference between groups: Differences between groups will be analyzed using Pearson's X^2 test or Fisher's exact test when expected values are less than 5.

The level of difference to consider significance will be an α of 0.05 or less.

For the reporting of adverse events, participants who were randomly assigned to an intervention group after application of the investigational product will be considered.

The final results report will be displayed in tables or graphs, as appropriate.

The investigational product will be considered safe when there are no clinical and statistical differences in all primary outcome variables, with respect to its comparator (Healon EndoCoat®).

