15.1 OVD performance evaluation

OVD performance evaluation

Identification card	
Study No. SOPH149-0220-I	Date: //
Subject's initials: _____	Subject No.: 149- _____ - _____

Directions:

This questionnaire must be answered by the surgeon immediately after completing the surgical procedure.
For each question, circle your answer.

Where:

0=very bad; 1=bad; 2=acceptable; 3=good; 4=very good

1 How do you consider the ability of the OVD to form and maintain the AC during CCC and IOL implantation?

0 1 2 3 4

2 How do you rate the ability of the OVD to be retained during phacoemulsification?

0 1 2 3 4

3 How do you consider the overall ease of use of the OVD?

0 1 2 3 4

4 How do you rate the ergonomics of the OVD?

0 1 2 3 4

5 How do you consider the transparency of the OVD during surgery?

0 1 2 3 4

6 How do you consider the ease of withdrawing the OVD from the AC?

0 1 2 3 4

References

- [1] S. Arshinoff, "Ophthalmic Viscosurgical Devices," Kohnen T., Koch DD (eds) *Cataract and Refractive Surgery. Essentials in Ophthalmology.*, Berlin, Heidelberg, Springer, 2005, pp. 3762.
- [2] BE, "Sodium hyaluronate and viscosurgery," from *Healon (sodium hyaluronate): a guide to its use in ophthalmic surgery*, New York, Wiley, 1983, pp. 5–28.
- [3] American Academy of Ophthalmology, "Lens and Cataracts," from *Basic and Clinical Science Course*, San Francisco, AAO, 2016, pp. 98–99.
- [4] H. Bissen-Miyajima, « Ophthalmic viscosurgical devices, » *Curr Opinion Oftalmol*, no. 50-54, p. 19, 2008.
- [5] T. (. Mang, « Rheology», from *Encyclopedia of Lubricants and Lubrication.*, Berlin, Heidelberg, Springer, 2014.
- [6] American Academy of Ophthalmology, Lens and Cataracts. Basic and Clinical Sciences Course, AAO, 2015.
- [7] National Eye Institute, "NEI", NIH, [Online]. Available : <https://nei.nih.gov/eyedata/cataract>. [Last accessed: July 4, 2016].
- [8] G. Brian and H. Taylor, "Cataract Blindness: Challenges for the 21st Century," *Bull World Health Organ*, vol. 79, no. 3, pp. 249-256, 2001.
- [9] H. Limburg, F. Barria -von -Bischhoffshausen, P. Gomez et al., «Review of recent surveys on blindness and visual impairment in Latin America», *Br J Ophthalmol*, vol. 92, pp. 315-319, 2008.
- [10] S. Polack, D. Yorston, A. Lopez-Ramos et al., «Review of recent surveys on blindness and visual impairment in Latin America», *Br J Ophthalmol*, vol. 92, pp. 315-319, 2008.

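### Ordinal grades (cellularity, flare, surgeon rating) are tested by methods that ignore their order, and under the 2x2 rule of 10.1.2 no analysis cut-point is set

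*Combined protocol and SAP*

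**What the plan says.** Section 10.1.2 puts nominal and ordinal variables in one class: "The results of the nominal and ordinal qualitative variables will be presented in frequencies, proportions and percentages". It then gives the test format for that class: "Statistical analysis to identify significant differences in qualitative variables will be performed by creating 2x2 contingency tables". McNemar is used within arm, and Pearson chi-square or Fisher (for small expected counts) between arms. The rank tests in the same section are assigned to continuous quantitative variables only.

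The synopsis also names chi-square or Fisher for qualitative variables, but does not mention 2x2 tables. Table 3 does the same in its test column and labels cellularity, flare and the transsurgical evaluation as ordinal.

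The scales are:
- **Cellularity:** six grades (7.4.4.5, Table 4).
- **Flare:** five grades (7.4.4.5, Table 5).
- **Surgeon rating:** six items in Annex 15.1, each scored "0=very bad; 1=bad; 2=acceptable; 3=good; 4=very good". Section 7.4.4.7 agrees: "They will be graded on a 5-point scale".

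Two places come near a cut-point. In 7.4.4.5, values of 3 or more "for cellularity or flare should be reported as AE". In 3.3, the arms are compared "with the presence of cellularity in postoperative AC" and "with the presence of postoperative AC flare".

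**The concern.** A 2x2 table needs two categories, so five or six ordered grades have to be merged, and 10.1.2 does not say where. If the test is instead run on all grades, as the synopsis wording allows, no cut is needed. A Pearson chi-square still treats the grades as unordered labels.

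Two things are at stake. Power is lost in a trial of 18 eyes per arm. And on the 2x2 reading, whether the arms are said to differ on inflammation or surgeon rating can depend on a cut chosen once the data are in hand.

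**Working it through.** The plan gives no figure for this point, so there is none to reproduce. The check has a textual part and a simulation.

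**Is a cut-point adopted?**
- Grade 3 or higher (7.4.4.5) is a threshold for reporting an adverse event. It is not tied to the between-arm test.
- The objectives in 3.3 speak of presence, and Table 3 gives 0 as the normal value. Together these point to 0 versus above 0 for cellularity and flare, but 10.1.2 does not take this up.
- The questionnaire has no threshold of any kind.
- The possible cuts are therefore 5 for cellularity, 4 for flare and 4 for each questionnaire item.

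**Inputs from the plan.** 18 per arm (10.2.1), 14 per arm as the evaluable minimum (10.1.4), significance level 0.05 and the chi-square/Fisher rule (10.1.2). I took the tests as two-sided.

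**Assumptions.** Control-arm percentages on a 5-level scale, lowest grade first: middle 35/35/20/8/2, mild 60/25/10/4/1, severe 10/25/35/20/10. The other arm is shifted by a common odds ratio at every cut c:

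odds₁(grade ≥ c) = OR × odds₀(grade ≥ c)

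Each scenario has 20,000 simulated trials, with tie-corrected Mann-Whitney.

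**Power (%), OR 5:**

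| Distribution | n per arm | cut ≥1 | cut ≥2 | cut ≥3 | Mann-Whitney |
|---|---|---|---|---|---|
| middle | 18 | 37 | 70 | 38 | 73 |
| mild | 18 | 67 | 54 | 16 | 72 |
| severe | 18 | 2 | 37 | 70 | 73 |
| middle | 14 | 22 | 48 | 23 | 61 |
| mild | 14 | 46 | 34 | 8 | 61 |
| severe | 14 | 1 | 23 | 49 | 62 |

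Repeat runs at 18 per arm keep Mann-Whitney within about 70–74%. A Pearson chi-square on the full arm-by-grade table, the alternative reading, has about 43–47%.

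**Shift reversed (OR 1/5), 18 per arm, middle/mild/severe.** The presence cut (≥1) has about 69/45/39% and Mann-Whitney about 68/51/73%.

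**Why the presence cut swings so much.** In the severe case 90% of control eyes are already above 0, so the odds are 9.
- At OR 5 the odds are 45 and the proportion is 45/46 = 97.8%. The expected counts of 18 are 16.2 and 17.6, which leaves almost nothing to detect.
- At OR 1/5 the odds are 1.8 and the proportion is 1.8/2.8 = 64.3%, or 11.6 of 18.

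**Best-placed cut against Mann-Whitney (upward shifts, OR 3 and 5).** On the 5-level scale it is within 5 points at 18 per arm and 7–15 points lower at 14 per arm. On an assumed 6-grade scale it is 6–7 points lower at 18 per arm and 13–16 lower at 14.

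**No true difference, one visit: chance that at least one cut is significant.**

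| Scale | 18 per arm | 14 per arm |
|---|---|---|
| 5-level | 7–10% | 4–5.5% |
| 6-grade | 10–12% | 5.5–7% |

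Mann-Whitney gives about 5%.

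**The case against.** The best defence is that 10.1.2 is loosely worded. The synopsis and Table 3 name chi-square or Fisher with no 2x2 limit, so an analyst could use all grades and need no cut. This stands against a claim a reader might infer, that the plan forces dichotomisation: the documents are inconsistent on it. It does not rescue the method, because the arm-by-grade chi-square ignores order and has the lower power shown above.

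Second, presence in 3.3 with a normal value of 0 arguably supplies the cut for cellularity and flare. That is a fair reading, but it leaves the questionnaire without one. A reader might also take the 2% figure to mean that the presence cut is nearly useless. That holds for one assumed distribution and one direction only. In the middle distribution with the shift reversed, the presence cut does as well as Mann-Whitney.

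Third, section 10.1.1 blinds the statistical staff to arm. This limits choosing a cut to favour one product, but does not prevent choosing on the p-value. At 14 per arm, free choice of cut at one visit inflates false positives little or not at all.

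Fourth, no main post-operative visit is named for cellularity and flare. This is missing detail, common for secondary outcomes in a pilot, and changing the test does not cure it. It is not part of the main point.

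Finally, a reader might infer from 7.5.1.1 that cellularity and flare are graded at scrutiny. That section refers to the general examination in 7.4.4.3, not to the grading in 7.4.4.5. Nor should anything rest on individual cells of Table 3's test column, which may have shifted when the PDF was read.

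**Conclusion.** The point holds as a minor one. Whether 10.1.2 or the synopsis governs, the planned test ignores the order of the grades. If 10.1.2 governs, no analysis cut-point is adopted.

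Under the assumed distributions a rank test on the full grades has higher power than the arm-by-grade chi-square, and its result does not depend on a cut. A well-placed cut comes close to it on a 5-level scale at 18 per arm, but is generally lower at 14. These sizes depend on assumed distributions and odds ratios.

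The effect is confined to secondary and exploratory outcomes. The safety conclusion in 10.1.2 rests on the primary variables alone, and the grade frequencies will be reported in any case. A reader might infer that the safety conclusion is at risk; the documents do not support that.

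**What to change.** In 10.1.2, the synopsis and Table 3, state that cellularity, flare and each questionnaire item are compared between arms by Mann-Whitney on the full grades. Add Wilcoxon signed-rank within arm for cellularity and flare. Keep chi-square or Fisher for adverse events (yes/no) and for a supplementary table of grade 3 or higher.

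Three accompanying edits do not carry the point:
- Name one main post-operative visit for cellularity and flare.
- After checking the source document, reconcile their baseline visit, which the within-arm test needs. Table 3 puts it at scrutiny and the study schedule (1.3) at scheduling.
- Reconcile the surgeon-rating range. Table 3 runs from 0 to 5 ("Bad (0) / Very good (5"), while 7.4.4.7 and Annex 15.1 use 0 to 4.

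The cost is a few lines of text. Both rank tests are already in the plan, and the data and software do not change. The drawback is that a rank test gives no simple percentage difference; the supplementary table supplies one for cellularity and flare.

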2.2.2 Safety of the investigational product

In the same clinical study described above, safety was evaluated by the cumulative rate of intraocular pressure (IOP) peaks ≥ 30 mmHg and the presence of adverse events (AEs).

The results demonstrated that the percentage of subjects with IOP spikes in the Healon® EndoCoat group was not higher than that in the Viscoat® group (cumulative percentage of subjects with IOP ≥ 30 mmHg during the study ($p = 0.0003$, $\delta = 0.13$, 90% confidence interval [-1.74, 7.72]).

Surgical complications reported were 3% (6/200) in the Healon® EndoCoat group and 8% (16/200) in the Viscoat® group.

Regarding AEs, 39 subjects reported an AE during the study. None of these were considered unexpected. Ninety-two percent of the AEs were IOP ≥ 30 mmHg; the incidence of this AE was 10.5% in the Healon® EndoCoat group and 7.5% in the Viscoat® group. The three AEs that did not correspond to an increase in IOP included: one subject in the Healon® EndoCoat group who developed cystoid macular edema (requiring treatment) and two subjects in the Viscoat® group: one subject who required IOL exchange for haptic damage and one who underwent removal of an ocular surface foreign body. None of the above AEs were considered related to OVD use. [21]

List of incidents or adverse reactions reported with a 3% sodium hyaluronate viscoelastic or with the use of intraocular sodium hyaluronate: [21] [22]

- Eye inflammation (iritis, hypopyon, endophthalmitis)
- Increased intraocular pressure
- Corneal edema
- Secondary glaucoma
- Corneal decompensation

All of the described incidents or adverse reactions may potentially occur with the use of PRO-149 or Healon® EndoCoat. [21] [22]

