7.4.2 Secondary outcome variables

- Incidence of adverse events.
- Changes in corneal thickness.
- Cellularity in AC.
- Flare in AC.
- Best corrected visual acuity

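### Adverse-event incidence is compared between arms by p-values only; at 18 per arm these cannot show similarity, and confidence intervals from the same counts would show what remains open

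*Combined protocol and SAP*

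**What the plan says.** Section 3.3 lists first among the secondary objectives a comparison of the two devices "with the incidence of AEs", and section 7.4.2 names "Incidence of adverse events" as a secondary outcome.

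The planned analysis of that outcome is in two places:

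- **Section 10.1.2.** "The results of the nominal and ordinal qualitative variables will be presented in frequencies, proportions and percentages". The between-group comparison is then a test: Pearson's chi-square, or "Fisher's exact test when expected values are less than 5". On significance: "The level of difference to consider significance will be an α of 0.05 or less".
- **Table 3 (section 7.4.4).** AEs have two rows. The number of cases is compared by Student t or Mann-Whitney U. Present/absent is compared by chi-square or Fisher's exact test.

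Neither place plans a confidence interval for AE incidence, and none is planned for any other outcome. The only intervals in the document are background results of the comparator's 400-patient trial (sections 2.2.1 and 2.2.2). No power or detectable difference is given for AEs.

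The alternative hypothesis in section 3.5 is that PRO-149 is equivalent in safety to Healon EndoCoat.

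**The concern.** A test for a difference can show that two arms differ. When it is not significant it does not show that they are alike, and in a small sample it is often non-significant even when a real excess exists. Here the hypothesis is equivalence in safety, the sample is 18 per arm, and every inferential output for AEs is a p-value from a difference test.

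Section 2.3.1 states that PRO-149 has no earlier clinical trial data, so the AE table is one of the study's main products. If it is summarised by p-values alone, a reader has no direct way to see how large an excess the data still allow. The matter at stake is how a stated objective is interpreted. No decision rule depends on it.

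**Working it through.** **Inputs**
- Arms: 18 per arm, 1:1 (sections 10.2.1 and 7.3).
- Alpha 0.05 (section 10.1.2). Sidedness is not stated; two-sided is assumed because the plan tests for differences.
- Test rule: Fisher if any expected count is below 5, otherwise Pearson chi-square without correction.
- Baseline: of IOP at or above 30 mmHg in the Healon EndoCoat arm of the cited trial, section 2.2.2 says "the incidence of this AE was 10.5" per cent. Section 7.4.4.2 makes the same finding an AE in this trial. It is one event type; the rate of any AE under this protocol is not given, so a range is shown below.

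**The plan's own figure.** The step from 14 to 18 reproduces: 14 / (1 - 0.20) = 17.5, rounded up to 18. The 14 does not follow from the stated margin. With p = p0 = 0.0697 (p0 is not given, so this is assumed), 0.0697 × 0.9303 × ((1.645 + 1.282) / 0.05)² is about 222. That is a separate matter, and only the planned 18 per arm is needed here.

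**Where significance starts at 18 per arm**
- 0 against 5: smallest expected count 2.5, so Fisher. p = 2 × C(18,5) / C(36,5) = 2 × 8,568 / 376,992 = 0.0455.
- 1 against 7: smallest expected count 4, so Fisher, p = 0.0408.
- 2 against 8: smallest expected count exactly 5, so chi-square. 36 × (8×16 - 10×2)² / (18×18×10×26) = 4.985, p = 0.026. Fisher would have given 0.060.

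**Power.** Sum Bin(a; 18, p1) × Bin(b; 18, p2) over every pair (a, b) for which the plan's rule gives p ≤ 0.05.

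| True rates | Power, plan's rule | Missed | Power, Fisher throughout |
|---|---|---|---|
| 10.5% v 21% | 7.0% | 93% | 6.5% |
| 10.5% v 31.5% | 25.8% | 74% | 22.0% |
| 10.5% v 42% | 54.3% | 46% | 45.6% |

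**Dependence on the baseline.** A tripling under the plan's rule is missed as follows:
- 5% v 15%: 95%
- 7.5% v 22.5%: 87%
- 9.75% v 29.25%: 78% (baseline 39/400, all AEs in the cited trial)
- 15% v 45%: 51%
- 20% v 60%: 26%

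**What intervals from the same counts would show**
- Newcombe 95% interval: lower limit = d - √[(p1 - l1)² + (u2 - p2)²], upper limit = d + √[(u1 - p1)² + (p2 - l2)²], where l and u are Wilson limits. For 2/18 these are 0.0310 and 0.3280; for 6/18, 0.1628 and 0.5625.
- 2/18 v 2/18: d = 0, p = 1.0, half-width √(0.0801² + 0.2169²) = 0.231. Interval about -23 to +23 points.
- 6/18 v 2/18, an observed tripling: d = 0.2222, smallest expected count 4, Fisher p = 0.23. Lower limit 0.2222 - √(0.1705² + 0.2169²) = -0.054; upper limit 0.2222 + √(0.2292² + 0.0801²) = 0.465. Interval about -5 to +46 points.
- 0/18, exact two-sided 95%: 0 to 1 - 0.025^(1/18) = 18.5%.

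**The case against.** The strongest reply is that this is a declared pilot, that AEs are secondary, and that no decision hangs on the AE test. Section 10.1.2 ties the word safe to the primary variables alone. Percentages per arm will be reported, so an imbalance will be visible, and IOP is itself a primary variable measured at each postoperative visit. Nothing in the plan says that p > 0.05 will be written up as no difference in AEs. All of this stands and limits the weight of the point. It does not remove it: a small pilot has most to gain from estimates with intervals, and the plan leaves open how a non-significant AE test is to be read against an equivalence hypothesis.

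Some stronger readings are tempting, but the documents do not support them:

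- *Chi-square or Fisher is the only AE comparison.* Table 3 also tests the number of events by Student t or Mann-Whitney U. The accurate statement is that all AE comparisons are p-values without intervals.
- *A tripling is missed about four times in five at this sample size.* At 10.5% that is roughly the figure for Fisher throughout (78%). The plan's mixed rule gives 74%, and the miss rate falls sharply at higher baselines. The protocol's AE definition is broad (sections 7.4.4.3 and 8.2), so the any-AE rate may well differ from 10.5%.
- *Non-significance is all but certain.* That fits a doubling from 10.5% (93%), but not a quadrupling (46%).
- *The AE comparison may rest on 14 per arm.* Sections 10.1.3 and 10.1.4 keep all exposed subjects, including those later replaced, in the safety analysis. Fourteen is the evaluable number before allowance for losses, not the AE denominator.

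**Conclusion.** The point holds as a reporting gap in a stated objective, and it is worth correcting. AE incidence is compared by p-values alone, and at 18 per arm a non-significant result cannot support equivalence in safety. At the quoted 10.5% baseline, a tripling would be missed about three times in four; equal counts of 2 per arm would still leave an excess of about 23 points open.

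The power figures rest on a two-sided 0.05 test, the plan's chi-square/Fisher rule, 18 exposed subjects per arm, and a baseline from one event type in an earlier trial. The interval examples need no assumed baseline. A reader might infer that the AE test could wrongly certify PRO-149 as safe; section 10.1.2 does not support that, because AEs do not enter that rule.

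**What to change.** In section 10.1.2 and the present/absent AE row of Table 3, specify for all exposed subjects:

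- the proportion with any AE in each arm, with an exact (Clopper-Pearson) 95% interval;
- the risk difference, PRO-149 minus Healon EndoCoat, with a Newcombe 95% interval;
- the same two summaries for any serious AE and for IOP of 30 mmHg or more, both of which are already recorded.

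State that the AE conclusion is drawn from the interval for the difference and that p > 0.05 is not read as no difference. Chi-square or Fisher can stay as a supplementary figure.

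The cost is a few lines in the plan and a short calculation on counts already collected, with no additional subjects or visits. The real price is wording: the AE conclusion will have to state how large an excess remains possible and so will read less favourably.

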3.5 Hypothesis

H_1 : PRO-149 viscoelastic solution is equivalent in safety to Healon® EndoCoat for use as an OVD in phacoemulsification surgery and IOL placement in patients with senile cataracts.

H_0 : PRO-149 viscoelastic solution is not equivalent in safety to Healon® EndoCoat for use as an OVD in phacoemulsification surgery and IOL placement in patients with senile cataract.

4. Study design

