10.1.4 Deviations from the statistical analysis plan

According to the sample size calculation to meet the study objective, 28 evaluable subjects (14 cases per arm) are required. If this number is not met due to a loss of subjects exceeding the 20% threshold established in this protocol (loss to follow-up or withdrawal from ICF), the sponsor may substitute these subjects to balance the treatment groups.

The results obtained from the replaced subjects will continue to be used for safety analysis and will be part of the ITT.

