10.2.2 Justification of the sample calculation

Although there are no references on sample size calculation for pilot studies, it was considered appropriate to perform the calculation based on the clinical study by Storr-Paulsen et al [48], who compared the influence of three OVDs of 1%, 2% and 3% SH on corneal endothelial cell count during cataract surgery up to three months postoperatively. All three OVDs showed a decrease in postoperative cell count, for SH-1% it was 18.46%, for SH-2% it was 18.03% and for SH-3% it was 6.97%. [48]

The percentage decrease in dispersive OVD at 3% SH was considered. The sample size was calculated using the equation for an equivalence ratio [49], which is useful when we want to test whether a ratio p , is different from a standard reference value, p_0 . In this case, we want to test that PRO-149 is equivalent to its comparator (Healon® EndoCoat). Here the test falls on PRO-149; that is, equivalence is represented by the alternative hypothesis (H_1), rather than the null hypothesis (H_0).

Working hypothesis for calculating the sample size:

$$H_0: |P - P_0| \geq \delta$$
$$H_1: |P - P_0| < \delta$$

Considering an $\alpha = 0.05$ corresponding to the type I error (95% confidence level), a power (β) = 0.20 corresponding to the type II error (80% power) and a test margin (δ) of 5%. The calculation to estimate the sample size was performed using an online tool (*Sample size calculators*, <http://powerandsamplesize.com>), following the following equations:

$$n = p(1-p) \left(\frac{Z_{1-\alpha} + Z_{1-\beta/2}}{|p - p_0| - \delta} \right)^2$$

$$1 - \beta = 2[\Phi(z - z_{1-\alpha}) + \Phi(-z - z_{1-\alpha})] - 1, z = \frac{|p - p_0| - \delta}{\sqrt{\frac{p(1-p)}{n}}}$$

Where:

n: sample size,

p₀: comparison value,

Φ: function of the standard normal distribution

Φ⁻¹: normal standard quantile function

α: Type I error

β: Type II error (1-β is the power)

δ: test margin.

According to the previous calculation, the result was 14 cases (eyes) per arm; this calculation was increased by 20% to account for potential losses. The total sample size required is 18 cases (eyes) per treatment arm, a total of 36 cases. This calculation is consistent with the sample size used in similar clinical studies where OVDs were employed. [50, 51, 52]

11. Ethical considerations

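### The hypothesis is equivalence, but section 10.1.2 declares PRO-149 safe when difference tests find nothing, with no clinical threshold and no confidence interval set against a margin

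*Combined protocol and SAP*

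**What the plan says.** Section 3.5 and the synopsis (1.1) state H1 as "PRO-149 viscoelastic solution is equivalent in safety to Healon® EndoCoat". Section 10.2.2 repeats this formally, with H0 that the absolute difference is at least δ and H1 that it is smaller, and notes that "equivalence is represented by the alternative hypothesis". A 5% margin is given there, for a proportion. The stated outcome of the calculation is that "the result was 14 cases (eyes) per arm", raised to 18 for losses, and 10.1.4 repeats that "28 evaluable subjects (14 cases per arm) are required".

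The analysis is of another kind. For normally distributed data, section 10.1.2 says "differences between groups will be analyzed using Student's t-test for independent groups"; otherwise Mann-Whitney is used. The synopsis and Table 3 (7.4.4) likewise list only difference tests for endothelial cell count and IOP. The decision sentence that closes 10.1.2 is: "The investigational product will be considered safe when there are no clinical and statistical differences in all primary outcome variables".

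**The concern.** Failing to reject no difference is not the same as rejecting a difference of δ or more. The planned tests address the first hypothesis, and the stated H1 needs the second. Following the plan to the letter can therefore give a verdict of safe that does not support H1.

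The incentive also runs the wrong way. The statistical part of the rule becomes easier to pass as the trial gets smaller or the measurements noisier. The clinical part has no stated size, so it could be settled after the results are known. This sentence carries the trial's main conclusion for a device that, by section 2.3.1, has no earlier clinical data.

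**Working it through.** **1. Is a margin used anywhere in the analysis?** The 5% appears only in 10.2.2 and is not carried into 10.1.2. Section 10.1.2 reports means, SDs and ranges, with no interval for the treatment difference. The normal ranges in Table 3 and the 30 mmHg IOP value in 7.4.4.2 apply to individual subjects and are not between-arm criteria.

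**2. Can the 5% simply be inserted into 10.1.2?** The formula in 10.2.2 is n = p(1−p)[(Z(1−α) + Z(1−β/2)) / (|p−p0| − δ)]². I take p = p0 = 0.0697, the cited loss for 3% hyaluronate; equality of p and p0 is my assumption. Then (1.645 + 1.282)² = 8.564, and:
- δ = 0.05: 0.0697 × 0.9303 × 8.564 / 0.05² = 222.1
- δ = 0.20: 0.0697 × 0.9303 × 8.564 / 0.20² = 13.9

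The stated 14 per arm is not reproduced at 5%; it corresponds to a 20% margin. That is a separate sample-size problem, but it means the 5% cannot be carried across unexamined.

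**3. How often would the cell-density test miss a 5-point excess loss?** Three assumptions are needed:
- The 5% is read as percentage points of mean cell loss. Table 3 records cells/mm², so percent change is my choice of scale.
- The t-test is two-sided at 0.05; the plan does not state sidedness.
- The documents give no SD. One can be back-calculated from the 90% interval [0.23, 4.33] in 2.2.1, if all 200 per arm were analysed: SE = (4.33 − 0.23)/(2 × 1.645) = 1.246, and SD = 1.246/√(2/200) = 12.46. That study compared Healon EndoCoat with Viscoat at 3 months; this trial measures at day 29. A range of 4 to 15 is therefore shown.

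The probability of non-significance comes from the noncentral t distribution with 2n−2 degrees of freedom and noncentrality 5/(SD√(2/n)):

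| SD (points) | 18 per arm | 14 per arm |
|---|---|---|
| 4 | 4.6% | 11% |
| 5 | 17% | 28% |
| 6 | 32% | 44% |
| 12.46 | 78% | 82% |
| 15 | 84% | 86% |

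At SD 12.46 the figure falls to 49% with 50 per arm, 19% with 100 and 2% with 200.

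**4. What do the other parts of the rule do?** These figures are for 18 per arm.
- *IOP.* Adding one to three independent IOP tests with no true IOP difference, at SD 12.46, gives 0.784 × 0.95 = 0.745 down to 0.784 × 0.95³ = 0.67. Independence is a simplification for repeated readings on the same eyes.
- *Clinical limit.* If a limit on the observed cell-loss difference is added to the t-test instead (by simulation):

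| Limit on observed difference | SD 12.46 | SD 6 |
|---|---|---|
| under 5 points | 49% | 32% |
| under 2 points | 19% | 7% |
| under 1 point | 9% | 2% |

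**5. What would an interval rule do?** Requiring the 90% interval to lie within ±5 points would pass a true 5-point difference at most about 5% of the time, whatever the SD. The expected half-width is t(0.95, 2n−2) × √(2/n) × SD, which is 0.564 SD at 18 per arm and 0.645 SD at 14. At SD 12.46 that is 7.0 and 8.0 points. For identical products:
- the ±5 rule is met in under 0.1% of trials at SD 12.46, and in 80% (18 per arm) or 65% (14 per arm) at SD 5;
- a one-sided 5-point non-inferiority rule at SD 12.46 is met in 32% or 27%.

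**The case against.** The rule does not rest on significance alone. It requires no clinical and no statistical difference, in both primary outcomes, so the chance of a safe verdict is lower than the t-test figures. That is right, and step 4 shows it. It does not rescue the rule, because the clinical part has no size and the result depends on which limit is chosen.

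The figures also rest on a scale and an SD that the plan does not supply. This stands too: 78% is an illustration and should not be quoted as the trial's error rate. The mismatch between hypothesis and decision rule does not depend on it.

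Finally, this is a pilot, which section 4.2 describes as smaller than a pivotal trial. That justifies a small sample and supports recasting the aim as estimation. It does not justify a pass/fail safety verdict based on non-significance.

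**Conclusion.** The concern holds and must be fixed. The plan sets out to prove equivalence, tests only for differences, and treats their absence as proof of safety. The probability of calling a worse device safe is not controlled. For a true 5-point excess cell loss it can lie below 5% or, on the t-test alone, above 80%, depending on the SD, the number of evaluable eyes and an undefined clinical judgement. The size rests on reading the 5% as percentage points and on the assumed SDs; the logical fault rests on neither. Nothing can be computed for IOP, because the documents give no IOP margin and no SD.

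**What to change.** **Preferred, and suited to a pilot.** Replace the last sentence of 10.1.2 with wording such as:

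> The between-arm difference in percent change in endothelial cell density (scrutiny to final visit) and in IOP will be reported with 90% confidence intervals. Non-significance of a difference test will not be taken as evidence of safety or equivalence, and no such conclusion will be drawn from it.

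The text should also name the IOP visit, whether IOP is analysed as level or change, the analysis population (10.1.3 and 10.1.5 name different ones) and the interval method for non-normal data. Restate the aim as estimation in 1.1, 3.5, Table 3 and 10.2.2, and bring 10.1.4 and 10.2.1 into line. Justify the sample size by precision: an expected 90% half-width of 0.56 SD at 18 per arm and 0.64 SD at 14.

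**If a claim is kept.** Before outcome data are seen, choose equivalence or non-inferiority. Fix the margin, scale and visit for each primary outcome, and reconcile the 5% with 14 per arm. Make the claim only if the interval lies within the margin (for non-inferiority, on the harmful side only). For ±5 points, 80% power and no true difference, 2 × 8.564 × SD²/5² gives about 107 evaluable per arm at SD 12.46, and 18 to 155 over SDs of 5 to 15.

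**Cost.** The preferred option needs no new visits or measurements, but it is an amendment that goes through the committees and COFEPRIS under 11.2. The real cost is losing the safe verdict. Little is lost if the SD is near 12.5, where a ±5 claim is almost unattainable at this size; more is lost if it is near 5.
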